5.3. Adjustments for Covariates

Analyses of all efficacy variables and patient-reported outcome variables defined in Sections 5.2.1.1 and 5.2.1.3 will be stratified using the randomization stratification factors listed below (defined based on IWRS data). Sensitivity analyses may also be performed to include additional stratification factors, non-stratified, or covariate adjusted analyses (for example, Cox models with covariates).

- Number of prior systemic therapies for advanced/metastatic disease (0 versus ≥ 1)
NOTE: Any therapy administered in the adjuvant/neoadjuvant setting will not be considered as a prior line of therapy here.
- Histological tumor type (LMS versus liposarcoma versus pleomorphic sarcoma versus other STS types)
- ECOG performance status (0 versus 1)

Prospectively planned sensitivity, subgroup, and multivariate analyses are described in more detailed in Section 5.11.4.

Other baseline covariates that may be of interest include (but may not be limited to) the following:

- liver lesions (presence at baseline vs. absence at baseline)

- lung lesions (presence at baseline vs. absence at baseline)
- sex (females vs. males)
- age
- weight
- duration of disease since diagnosis
- grade of STS at diagnosis (1/low vs. 2/intermediate vs. 3/high)
- albumin level
- prior systemic therapy in the adjuvant or neo-adjuvant setting (none vs. any)
- prior systemic anti-cancer therapy (none vs. any)
- alanine aminotransferase (ALT)
- bone lesions (presence at baseline vs. absence at baseline)
- prior radiation therapy (none vs. any)
- duration of most recent prior systemic therapy
- hemoglobin
- platelets
- leukocytes

5.4. Handling of Dropouts or Missing Data

Rules for handling dropouts or missing data are listed by type of analysis alphabetically. Unless otherwise specified, observed data will be used and missing data will not be imputed or carried forward.

In the event that the date of second disease progression (disease progression occurring during post-study systemic anticancer therapy) is reported only to the nearest month, the date will be imputed for analysis (assumed to have occurred on the 15th day of the reported month).

General rules for imputing dates related to AE or concomitant therapy:

- Onset date of an AE or start date of a concomitant therapy:
 - If only the day is missing, the date will be set to:
 - First day of the month that the event occurred, if the onset yyyy-mm is after the yyyy-mm of first study treatment.
 - The day of the first study treatment, if the onset yyyy-mm is the same as yyyy-mm of the first study treatment.
 - The date of informed consent, if the onset yyyy-mm is before the year and month of the first treatment.
 - If both the day and month are missing, the complete date will be set to:
 - January 01 of the year of onset, if the onset year is before/after the year of the first study treatment.
 - The date of the first dose, if the onset year is the same as the year of the first study treatment.

- The date of informed consent, if the onset year is before the year of the first treatment.
- Resolution date of an AE or end date of a concomitant therapy:
 - If only the day is missing, the date will be set to the last day of the month of the occurrence, or to the date of death if the patient died in the same month.
 - If both the day and month are missing, the date will be set to December 31 of the year of occurrence or to the date of death if the patient died in the same year.

If an onset date for an AE is missing, then the AE will be considered treatment emergent with unknown onset date.

General rule for imputing other dates: If a date variable is needed for an analysis, use the following general rule to impute incomplete date:

- If only the day is missing, then assign Day 15 of the month, or the date of death if the patient died prior to 15th of the same month to the day.
- If month is missing, then the date will be set to July 1st of the year, or the date of death if the patient died prior to July 1st of the same year.

However, after imputation, check if the imputed date is logically consistent with other relevant date variable(s) and make appropriate correction if necessary. For example, if a visit start date was 16 May 2008 and a tumor assessment date was xx May 2008 (missing day) but it was known that it occurred on or after that visit, then after imputation, the tumor assessment date became 16 May 2008. In this case, the imputed tumor assessment date should be compared to the visit start date and then corrected to be the later of the 15th day of the month and the visit start date.

Patient-reported outcome analysis: For percentage compliance of the mBPI-sf, EORTC QLQ-C30, and EQ-5D-5L, instruments with at least 1 item completed will be considered as having been completed. Please refer to Section 5.13 for additional details.

Safety analysis: The following rule for missing data processing will apply for safety analysis:

- Missing classifications concerning study medication relationship will be considered as related to study medication (both components).
- If the AE onset date is missing or partial, the date will be compared as far as possible with the date of first dose of study medication when determining whether or not the AE is present at baseline. In this case, the AE will be assumed to be treatment emergent, unless there is clear evidence (through comparison of partial dates) to suggest that the AE started prior to the first dose of study medication.

Time-to-event analysis: All censored data will be accounted for using appropriate statistical methods. See Sections 5.2.1 and 5.11 for details.

5.5. Multicenter Studies

This is a multicenter, randomized, double-blind study. Due to the expected large number of investigative centers used for this study, investigative center was not used as a stratification factor and will not be used for covariate adjustment or subgroup analysis. Retrospective exploratory analyses of center-specific data or region-based subgroup analysis may be conducted as deemed appropriate to support global regulatory requests.

5.6. Multiple Comparisons/Multiplicity

The independent data monitoring committee (IDMC) will perform unblinded interim safety and efficacy analyses. Family-wise type I error is controlled for this study's key efficacy outcomes (OS, PFS, and ORR) as described in Section 12.1 of the study protocol and Section 5.11 of this SAP. Regarding all other study analyses, multiplicity of statistical error is not controlled or adjusted for in any way.

5.7. Study Patients

The following summaries (frequency and percentage) and listings for patient disposition will be performed:

- Patient disposition by investigator site and country and overall: patients entered (that is, signed informed consent), entered but not randomized, randomized (that is, ITT population), randomized but not treated, treated (that is, safety population), in Per-Protocol population, and eligible for PRO analysis (refer to Section 5.7.1 for analysis population definitions)
- The primary reasons for discontinuation from study treatment and patients still receiving treatment will be summarized by study treatment arm using frequency and percentage. The following discontinuation reasons will be presented: AE, PD (radiologically documented objective deterioration, symptomatic deterioration), death (due to AE, PD, or other), and other.
- Listings of:
 - primary reason for discontinuation from study regimen
 - date of randomization, first dose administration, last dose administration, and discontinuation from study regimen

5.7.1. Analysis Populations

Unless otherwise specified, all analyses will be based on the population of patients enrolled in the main protocol (Cohort 1). Patients enrolled under the extended enrollment addendum in Taiwan will be referred to as Cohort 2. Patients enrolled in Cohort 2 will not be included in the primary analysis of overall survival. As necessary, efficacy and safety analyses will be summarized for patients enrolled in Taiwan by pooling Cohort 1 and Cohort 2. All pooled analyses will be for descriptive purposes only.

[Table JGDJ.5.4](#) lists analysis population definitions and associated data type for analysis.

Table JGDJ.5.4. Analysis Populations

Population	Definition	Analysis Type / Variable	Note
Intention-to-treat (ITT) Population	All randomized patients	Baseline characteristics, concomitant medication, all efficacy analyses	Patients will be grouped according to randomized treatment.
Safety Population (SP)	All randomized patients who received any quantity of study drug	Safety, e.g. dosing/exposure, AE and resource utilization	Patients will be grouped according to treatment received as defined by the first dose received.
LMS subset of ITT Population	All randomized patients with LMS histologic subtype	Baseline characteristics, concomitant medication, all efficacy analyses	Patients will be grouped according to randomized treatment.

Abbreviations: AE = adverse event; ITT = intent-to-treat; LMS = leiomyosarcoma.

Compliance for the PRO instruments will be reported for the ITT population. All other PRO analyses will be on the ITT population and will include those from whom a completed PRO instrument was obtained at baseline and at least 1 postbaseline (either during study treatment period or 30-day postdiscontinuation follow-up period); thus, the actual patients included for each analysis will depend on the instrument and response variable.

A patient listing of analysis population details will be provided. This listing will be presented by treatment group and will include: investigator site, patient identifier, inclusion/exclusion flag for each population, and reason for exclusion from each population. All patients screened will appear on this listing.

Significant protocol violations that potentially compromise the data integrity and patients' safety will be summarized for the ITT population. These violations will include deviations that can be identified programmatically and those that can only be identified by the clinical research associate during monitoring. Significant protocol violations are described in the Trial Issue Management Plan within the study Trial Master File. The list of significant protocol violations to identify patients to be excluded from the Per-Protocol population will be defined prior to the final database lock.

5.8. Demographic and Other Baseline Characteristics

The following patient demographic and other baseline characteristics will be summarized:

- patient demographics: age (years) and age group (< 65 vs. ≥ 65), gender, ECOG performance status, country, race (White, Black, Asian, All Other), height (cm), weight (kg), and BSA (m²)
- potential prognostic factors as listed in Section 5.3
- baseline disease characteristics (at study entry): current disease stage, duration of disease (months)
- prior cancer therapies: type of therapy (surgery, radiotherapy, systemic therapy), type of prior surgery, type of prior radiotherapy, and type of prior systemic therapy

- historical illness (no versus at least 1 diagnosis) by Medical Dictionary of Regulatory Activities (MedDRA®) preferred term (PT), presented in decreasing frequency
Note. Subjects reporting more than 1 condition/diagnosis within a PT will be counted only once for that PT.
- comparison between the eCRF and interactive web response system (IWRS) values of the stratification factors

Patient listings of demographic data and baseline characteristics will be provided. Patient listings of prior cancer therapies (surgery, radiotherapy, and systemic therapy) will be provided.

5.9. Concomitant Medications

The following concomitant medications used in study treatment period or the 30-day postdiscontinuation follow-up period will be summarized by numbers and percentages by treatment group, presented in decreasing frequency of the World Health Organisation drug term across treatment arms:

- all concomitant medications
- premedication for study drug
- growth factors

The proportions of patients reporting use of concomitant medications will be compared between the treatment groups. Patient listing of all concomitant therapies and premedications will be provided. Additional exploratory analyses of impact of premedication use on the rate and severity of IRRs, of growth factors on rates of neutropenia and febrile neutropenia, and of dexrazoxane use on the rate and severity of cardiac dysfunction will be considered.

5.10. Treatment Compliance

Olaratumab/placebo and doxorubicin will be intravenously administered only at the investigational sites. As a result, patient compliance is ensured.

5.11. Efficacy Analyses

5.11.1. Group Sequential Testing Using Graphical Approach

The statistical testings will be conducted according to the graphical method of Maurer and Bretz (2013) so as to control the overall type I error rate at 0.025 (one-sided) or equivalently, 0.05 (two-sided). The graphical approach can be characterized by first defining a set of prespecified null hypotheses that are organized graphically by providing initial alphas for each hypothesis and weights for each edge of the graph that will determine the propagation of α through the entire hypothesis-testing scheme.

[figure not shown]
The hypotheses objectives are:

Primary objectives: H_{11} : OS in the LMS population

H_{12} : OS in the ITT population
 Secondary objectives: H_2 : PFS in the ITT population
 H_3 : ORR in the ITT population

Initially, the overall one-sided alpha of 0.025 is split between the primary objectives of OS in the LMS population (H_{11}) and OS in the ITT population (H_{12}), with H_{11} tested at a one-sided $\alpha_1=0.005$ and H_{12} tested at a one-sided $\alpha_2=0.02$. Zero alpha is initially assigned to the other hypotheses.

The initial graph with alpha at each node and weight for each edge is shown in [Figure JGDJ.5.1](#).

[figure not shown]

Abbreviations: ITT = intent-to-treat; LMS = leiomyosarcoma; ORR = overall response rate; OS = overall survival; PFS = progression-free survival. ϵ is set equal to 0.001.

Figure JGDJ.5.1. Initial graphical representation of testing sequence.

After rejection of any hypothesis, the graph will be updated on alphas at each node and weight at each edge, as described in Maurer and Bretz (2013).

It is valuable to note that the weight of the line from H_{11} to H_{12} is 1, indicating that H_{12} receives all of the alpha allotted to H_{11} if H_{11} is rejected, and similarly, the weight of the line from H_{12} to H_{11} is $1-\epsilon$, where ϵ is set equal to 0.001, indicating that H_{11} receives virtually all of the alpha allotted to H_{12} if H_{12} is rejected. Consequentially, after rejecting H_{11} and/or H_{12} , further testing essentially becomes a gatekeeping strategy to assess PFS and ORR in fixed sequence (except with an additional loop back from H_3), as illustrated below in [Figure JGDJ.5.2](#).

Abbreviations: ORR = overall response rate; OS = overall survival; PFS = progression-free survival. ϵ is set equal to 0.001.

Figure JGDJ.5.2. Graphical representation of testing sequence conditional on rejection of either H_{11} or H_{12} to illustrate updating of alphas at each node and weight at each edge.

Assigning $\epsilon=0.001$ initially focuses virtually all the alpha on the primary endpoints. The iterative process of subsequent updating of the graph and redistribution of α is described in [Table JGDJ.5.5](#) below and is repeated until no further hypotheses can be rejected.

Table JGDJ.5.5. Planned Alpha Spending Using Graphical Approach

Test	Node α at Analysis
1. Initial Graph (Figure JGDJ.5.1)	
LMS OS	0.005
ITT OS	0.02
2. Graph when H_{11} LMS OS is rejected (Figure JGDJ.5.2; left)	
ITT OS	0.025
2.1 PFS* (If ITT OS is further rejected)	0.025
2.1.1 ORR** (If PFS is further rejected)	0.025
3. Graph when H_{12} ITT OS is rejected (Figure JGDJ.5.2; right)	
LMS OS	0.02498
3.1 PFS* (if LMS OS is further rejected)	0.025
3.1.1 ORR** (if PFS is further rejected)	0.025
3.2. PFS* (if LMS OS is not rejected)	0.00002
3.2.1 ORR** (if PFS is further rejected)	0.00002

Abbreviations: ITT = intent-to-treat; LMS = leiomyosarcoma; ORR = objective response rate; OS = overall survival; PFS = progression-free survival.

* Information fraction for PFS events at 60% OS events interim is 82% based on design assumptions that PFS median for control arm is 4.5 months, and experimental arm is 7.15 months.

** Information fraction for ORR response at 60% OS events interim is 85% based on design assumptions that ORR in response time is 6 months for both arms, and response rate for control arm is 12% and for experimental arm is 19%.

5.11.2. Primary Efficacy Analyses

For the primary comparison of OS, the primary endpoint, between the assigned study treatment arms, a stratified log-rank test will be performed to test the following statistical hypotheses about the OS HR for olaratumab over placebo:

H_0 : OS HR ≥ 1.00 (Olaratumab not superior to placebo)

H_a : OS HR < 1.00 (Olaratumab superior to placebo)

The stratification will be based on IWRS data that used for randomization (see Section 5.3 for more details). An unstratified log-rank test will also be performed as sensitivity analysis.

The following analyses of OS will also be performed:

- Summary of OS events (number and percentage), censoring rate, and reasons for censoring
- Restricted mean difference in OS between the treatment groups and its 95% CI, with the area under the Kaplan-Meier survival curve calculated up to the minimum across treatment arms of the maximum observed (that is, event or censored) time
- Kaplan-Meier survival curve (Kaplan and Meier, 1958) by treatment group will be provided.
- The Kaplan-Meier method will be used to estimate parameters (medians, quartiles, and percentages), difference of percentage and associated 95% CI and p-values for time-to-event analyses on each treatment group at 3, 6, 9, 12, and 24 months. Patients who did not have the event at the corresponding time point will be considered right-censored observations.
- HR for treatment effect will be estimated using Cox proportional hazards (PH) model stratified identically to the primary log-rank test with assigned treatment as the only covariate, reported with 2-tailed 95% CIs and Wald's test p-value. This Cox PH model will be referred to as the primary Cox PH model henceforth.

5.11.3. Secondary Efficacy Analyses

5.11.3.1. Supportive Analyses of Primary Efficacy Endpoint

The following supportive analyses of OS will be performed:

- HR for treatment effect will be estimated using an unstratified Cox PH model.
- As a sensitivity analysis, the primary OS analysis will be repeated using stratification based on the eCRF values.
- HR for treatment effect will be estimated using a multivariate Cox PH model, stratified by the randomization factors, with covariates selected among the additional factors listed in Section 5.3 using a stepwise selection method. Factors will be analyzed as continuous variables, except for those factors specifically identified with categories in Section 5.3. The stepwise selection will use an entry p-value <0.05 and exit p-value ≥ 0.10 . The “assigned treatment arm” variable will not be used within the stepwise procedure but rather added to the final model. The OS HR for treatment effect and corresponding 95% CI will be estimated from the final model. Any covariate listed in Section 5.3 may be removed from this planned analysis if the number of patients representing 1 level of that variable is insufficient or data collected on that variable are insufficiently complete.

- As a sensitivity analysis, the primary OS analysis will be repeated for the Per-Protocol population.
- To evaluate whether new anticancer treatment affects OS, a sensitivity analysis will be conducted censoring OS at a start date of new anticancer therapy.
- To evaluate whether the number of cycles of doxorubicin affects overall survival, a comparative OS sensitivity analysis will be conducted that excludes patients completing less than 4 cycles of doxorubicin (then repeated excluding those completing less than 5 cycles, then 6 cycles).
- Efficacy analyses (OS, PFS, and ORR) will be analyzed for a subset of patients who have received at least one dose of either olaratumab or placebo monotherapy after discontinuation of study treatment with doxorubicin. Baseline characteristics and drug exposure will be summarized as supportive analyses for this subgroup of patients receiving monotherapy.

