Patients will receive combination treatment for 8 cycles followed by monotherapy olaratumab or placebo until evidence of progressive disease (PD), unacceptable toxicity, death, or other withdrawal criteria are met. No crossover will be permitted.

Diagnosis and Main Criteria for Inclusion and Exclusions: Patients at least 18 years of age, ECOG PS 0 to 1, anthracycline naïve, with histologically confirmed, advanced or metastatic STS, and not amenable to treatment with surgical resection or radiotherapy with curative intent. Patients with gastrointestinal stromal tumor (GIST) or Kaposi's sarcoma will be excluded.

Test Product, Dosage, and Mode of Administration: Olaratumab: injection for intravenous (IV) use, supplied in single-use 500 mg/50 mL vials containing 10 mg/mL of product in histidine buffer, administered to patients as an IV infusion at a loading dose of 20 mg/kg on Days 1 and 8 in Cycle 1, followed by 15 mg/kg on Days 1 and 8 in subsequent cycles. Cycles are 21 days in length.

Reference Therapy, Dose, and Mode of Administration: Placebo: injection for IV use, supplied in single-use vials, administered to patients as an IV infusion on Days 1 and 8. Doxorubicin: commercial formulations will be used and administered intravenously. Doxorubicin (75 mg/m²) is to be administered on Day 1 of each 21-day cycle, for 8 cycles. Dexrazoxane: Commercially available dexrazoxane may be administered starting at Cycle 1 at a 10:1 ratio (dexrazoxane:doxorubicin) at the investigator's discretion, prior to the doxorubicin infusion for the prevention of cardiotoxicity and its use is recommended in patients receiving 5 or more cycles of doxorubicin. Dexrazoxane should be administered after completion of the olaratumab/placebo infusion, prior to administration of doxorubicin. Doxorubicin should be administered within 30 minutes of receiving dexrazoxane.

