8.1.1. Baseline and Study Treatment Period Assessments

Baseline radiographic assessment of disease will be performed within 28 days prior to randomization; scans performed prior to the date of consent may be used provided they are within 28 days of randomization.

Imaging and tumor assessment will be performed every 6 weeks (± 7 days), irrespective of treatment cycles, as calculated from randomization. Imaging requirements include CT scan or magnetic resonance imaging (MRI) of chest, abdomen, and pelvis. Other areas may be scanned, when clinically indicated. Digital images are to be sent to a third-party organization (TPO) for storage. It is recommended that CT imaging of the abdomen/pelvis be performed with IV contrast, whenever possible. If this is not feasible/advisable secondary to hypersensitivity or other conditions, then gadolinium-enhanced MRI is preferred. For patients with known serious allergic reactions to CT contrast material, a CT of the chest without contrast and contrast-enhanced MRI of the abdomen/pelvis are encouraged.

The patient's first treatment will be administered within 72 hours (3 days) following randomization. Patients in both arms will receive any necessary premedication if needed (see Section 9.1.1) prior to the infusion of study therapy at each treatment cycle.

A treatment cycle will be defined as 3 weeks (21 days \pm 3 days). The start of study treatment will be considered Cycle 1 Day 1 (C1D1).

Patients in the investigational **Arm A** will receive:

- Olaratumab on Day 1 and Day 8 of every 3-week cycle as an IV infusion over approximately 60 minutes, followed by a 1-hour observation period for the first 2 cycles. If there is no evidence of an infusion-related reaction (IRR) after the D1 and D8 infusions of olaratumab in the first 2 cycles, no observation period is required for subsequent treatment cycles. In the event that a Grade 1 or 2 IRR occurs after Cycle 2, the 1-hour observation period will be reinstated for a minimum of 2 cycles. The reinstated observation period may be suspended after 2 cycles if the patient shows no further signs or symptoms of an IRR.

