9.4. Selection and Timing of Doses

A cycle is defined as an interval of 21 days (up to 3 days delay of a cycle will be permitted due to holidays, weekends, bad weather, or other unforeseen circumstances and will not count as a protocol deviation).

Refer to Section 5.3.1 for the olaratumab dose rationale in this study.

The dose of olaratumab/placebo administered will be determined by measuring the patient's weight in kilograms on Days 1 and 8 of each cycle. The dose of doxorubicin administered will be determined by calculating the patient's body surface area (BSA) at the beginning of each cycle. If the patient's weight does not fluctuate by $\geq 10\%$ (increase or decrease) from the weight used to calculate the prior dose, the olaratumab/placebo dose will not need to be recalculated. A $\pm 5\%$ variance in the calculated total dose will be allowed for ease of dose administration.

Patients will receive combination treatment with olaratumab/placebo + doxorubicin for 8 cycles, followed by olaratumab/placebo as monotherapy until evidence of progressive disease (PD), unacceptable toxicity, death, or other withdrawal criteria are met.

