To maintain a concomitant administration schedule of olaratumab/placebo and doxorubicin on Day 1 of the first 8 cycles, a delay in olaratumab/placebo administration will be allowed to match the corresponding delay in doxorubicin due to toxicity. For the same reason, a delay in doxorubicin administration will be allowed to match the corresponding delay in olaratumab/placebo due to toxicity. Treatment may be delayed for up to 21 days (1 equivalent cycle) to allow a patient sufficient time for recovery from study drug-related toxicity. If a patient does not recover from the toxicity within 42 days (2 equivalent cycles) from last dose, then the patient must be discontinued from study therapy.

Dose Modifications:

Any patient who requires a dose reduction will continue to receive the reduced dose for the remainder of the study. Any patient who has had 2 dose reductions and who experiences a toxicity that would cause a third dose reduction must be discontinued from study treatment.

Since all investigators are blinded to treatment arms, they will treat all patients as if the patient received study drug versus placebo and will adjust doses accordingly.

In the event of an alteration in olaratumab/placebo dose due to an olaratumab/placebo-related toxicity, doxorubicin need not be altered, and the planned doxorubicin schedule should be maintained.

Similarly, olaratumab/placebo therapy need not be altered or discontinued for doxorubicin-related toxicity. An alteration in doxorubicin dose will always necessitate a corresponding change in dexrazoxane dose, if administered, in order to maintain a dosage ratio of 10:1 (dexrazoxane:doxorubicin).

Discontinuations:

In general, discontinuation of 1 study drug (olaratumab/placebo or doxorubicin) will not necessitate discontinuation of the other study drug. Any changes in treatments being added to or removed from patient care will be recorded on the eCRF.

In the event of discontinuation of olaratumab/placebo therapy due to an olaratumab/placebo-related toxicity, doxorubicin need not be altered, and the planned doxorubicin schedule should be maintained. In the event that olaratumab/placebo treatment is discontinued for reason of toxicity, the patient may continue treatment with doxorubicin through Cycle 8 at the discretion of the investigator.

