5.11.3.2. Key Secondary Efficacy Analyses

For PFS, the same analyses used for the analyses of the primary endpoint OS will be performed. In addition, as sensitivity analyses, the primary PFS analysis will be repeated using different PFS censoring rule as defined in [Table JGDJ.5.2](#), to evaluate whether and to what extent the conclusion of the PFS analysis under the primary definition would be affected under the different censoring rules.

This comparison of PFS using the same method as that for the primary analysis of PFS will be considered inferential only in case of significant results for OS analysis (that is, as a gatekept analysis so as not to inflate the overall type I error rate).

The main PFS analysis will also be repeated for a subset of patients started monotherapy.

If PFS analysis is significant, then testing on ORR will be conducted. Objective tumor response (CR+PR) rate (ORR) will be reported along with exact confidence bounds (CI: 95%) and compared using the Cochran-Mantel-Haenszel test adjusting for the stratification variables. A sensitivity sensitivity analysis on ORR will be performed to consider only confirmed response (using 4-week interval for confirmation).

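### The OS analysis that excludes patients by doxorubicin cycles completed does not test whether cycle number affects OS; it and the monotherapy subset compare arms among patients selected after randomization

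*SAP*

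**What the plan says.** SAP 5.11.3.1 (Supportive Analyses of Primary Efficacy Endpoint) states: "To evaluate whether the number of cycles of doxorubicin affects overall survival, a comparative OS sensitivity analysis will be conducted that excludes patients" with fewer than 4 completed doxorubicin cycles. The run is then repeated with thresholds of 5 and 6. The comparison is not defined further; between arms is the natural reading.

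The next bullet analyses OS, PFS and ORR in a "subset of patients who have received at least one dose of either olaratumab or placebo monotherapy after discontinuation of study treatment with doxorubicin". Section 5.11.3.2 adds: "The main PFS analysis will also be repeated for a subset of patients started monotherapy". The between-arm test is therefore stated for PFS and only implied for OS and ORR.

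SAP 5.2.1.1 counts OS from randomization. No landmark, delayed entry or caveat about post-randomization selection is given for these subsets. The caution in SAP 5.11.4 concerns chance variation between subgroups. SAP 5.6 leaves everything outside OS, PFS and ORR without multiplicity control.

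On cycles, Protocol 9.4 says "A cycle is defined as an interval of 21 days", and the synopsis says doxorubicin "is to be administered on Day 1 of each 21-day cycle, for 8 cycles". Neither document says whether a cycle is completed when the dose is given or when the 21 days have ended.

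**The concern.** Two things are wrong, and they are separate.

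- **The question is not addressed.** Cycle number enters only as an exclusion rule. It is not a covariate, a grouping factor or a time-dependent term.
- **The arms compared are no longer the randomized arms.** Completing 4 to 6 cycles, or reaching monotherapy, depends on not having progressed, died or stopped for toxicity. If that selection is related to prognosis and differs between arms, in amount or in mechanism, the between-arm hazard ratio can be biased.

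At stake is interpretation. A subset hazard ratio with a p-value, printed beside the primary OS result, could be read as evidence on doxorubicin exposure or on olaratumab monotherapy. It is neither.

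**Working it through.** **1. Plan figures.** No figure in the plan belongs to these subsets. The primary design reproduces: 4 × (2.054 + 0.842)² / (ln 0.723)² = 319 events, 322 events give 80.4% power at one-sided 0.02, and 322 / 0.70 = 460 patients. Nothing below alters it.

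**2. Can the trend over the three thresholds stand in for the missing contrast?** A simulation of 400,000 patients assumed a median OS of 16 months, a normal-copula PFS–OS correlation of 0.5, a true arm hazard ratio of 1.00, and stopping only at progression or death.

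| Setting | ≥4 cycles | ≥5 | ≥6 |
|---|---|---|---|
| Arm HR, no effect of cycles on OS | 1.08 | 1.09 | 1.11 |
| Arm HR, real effect of cycles (remaining survival × exp(0.1 per cycle)) | 1.11 | 1.14 | 1.16 |
| Control median OS, no effect of cycles (16.0 months in all patients) | 23.1 | 24.5 | 25.8 |

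The pattern has the same shape with and without a cycle effect. Even at correlation 0, the control median rises from 16.0 to 20.0 months at ≥6 cycles, from guaranteed survival time alone.

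**3. Retention implied by the SAP.** The footnote to Table JGDJ.5.5 gives "design assumptions that PFS median for control arm is 4.5 months, and experimental arm is 7.15 months". With exponential PFS, S(t) = 2^(−t/median) and t = days / 30.4375. At day 84, t = 2.760 months, so control is 2^(−2.760/4.5) = 0.654 and experimental is 2^(−2.760/7.15) = 0.765. Of 230 per arm, about 80 and 54 are no longer progression-free.

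| Day | Control | Experimental |
|---|---|---|
| 84 | 65% | 77% |
| 105 | 59% | 72% |
| 126 | 53% | 67% |
| 168 | 43% | 59% |

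This is progression-free status, not doxorubicin retention. Dose delays (Protocol 9.4.1.1) also blur the link between days and cycles.

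**4. Size of the bias under a true OS hazard ratio of 1.00.** Assumed, not in the documents: a shared gamma frailty (mean 1, variance v) on progression and death, OS median 14 or 20 months, 12-month uniform accrual and no dose delays. The total PFS hazard is (2^v − 1)/(v × median), which keeps the SAP's PFS medians. The data cut is at 70% deaths, with an unstratified Cox model.

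| Reading of a completed cycle | Subset | v = 0.25 | v = 0.5 | v = 1.0 |
|---|---|---|---|---|
| 21-day cycle ended (days 84/105/126) | ≥4 | 1.04 | 1.07 | 1.10 |
| | ≥5 | 1.05 | 1.08 | 1.13 |
| | ≥6 | 1.06 | 1.09 | 1.14 |
| Dose given (about days 64/85/106; progression known from the last six-weekly scan) | ≥4 | 1.02 | 1.03 | 1.05 |
| | ≥5 and ≥6 | 1.04 | 1.07 | 1.10 |

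A repeat run of the first reading reached 1.15 at ≥6 cycles with v = 1.0. The copula model, over correlations 0.3–0.7 and OS medians 12–20 months, gave 1.04–1.14 at ≥4 and 1.05–1.20 at ≥6. With no frailty the hazard ratio is about 1.00. For monotherapy after 8 cycles the frailty model gives 1.06 / 1.09 / 1.14 (day-126 scan) or 1.07 / 1.12 / 1.18 (day-168 scan).

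**5. Equal retention is not a safeguard.** If both arms stop by the same mechanism at the same rate, the result is about 1.00. Now equalize retention at day 84, but remove control patients through frailty-linked progression and experimental survivors at random. The hazard ratio becomes 1.07 / 1.13 / 1.23 (OS median 14 months), and up to 1.28 in another run.

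**6. Direction.** With equal PFS and prognosis-linked toxicity stops at assumed rates of 0.08 per month (experimental) and 0.03 (control), the hazard ratio is 0.93–0.98. With the PFS effect as well, it is 0.99–1.05. With a true ITT hazard ratio of 0.723 and the SAP's PFS medians, the subsets give 0.74–0.80.

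**7. Precision.** The 4–6 cycle subsets hold about 143–256 deaths. The 95% limits lie a factor exp(1.96 × 2/√d) from the estimate: 1.39 at d = 143 and 1.28 at d = 256. The null shifts in step 4 for these subsets are smaller than that.

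**The case against.** The strongest reply is that the aim is loosely worded rather than wrong. The preceding bullet in 5.11.3.1 uses the same idiom for new anticancer treatment and only censors at its start. Under a heading of supportive analyses of the primary endpoint, the natural intent is to ask whether the arm effect holds once short doxorubicin exposure is removed. That reading is fair, and rewording would cure the mismatch. It does not cure the selection, because the arms are still compared within groups formed after randomization.

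It is also fair that the bias figures are not document-based. Only the PFS medians come from the SAP, as a footnote on information fractions; the link to prognosis, the OS medians and the toxicity stops are assumed. Protocol 5.3 reports Grade 3 or higher events in 79.7% versus 69.2% in the phase 2 trial. That makes an imbalance plausible but is not a discontinuation rate.

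Four stronger readings are tempting, and the documents do not support them:

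- **That the primary conclusion is at risk.** These analyses carry no alpha and do not enter the primary tests.
- **That the subsets would manufacture a benefit.** Under the SAP's own OS and PFS assumptions they attenuate it.
- **That bias needs unequal retention.** Step 5 of the working shows otherwise.
- **That a landmark analysis of all patients alive could replace the cycle analysis.** It ignores cycles.

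**Conclusion.** The point holds. As written, the exclude-by-cycles analysis does not answer whether cycle number affects OS, and this rests on the text alone. As a robustness check, it and the monotherapy subset yield between-arm hazard ratios open to selection bias. The SAP's PFS medians make unequal selection the expected case.

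The size is uncertain. It is about 1.04–1.15 under a true hazard ratio of 1.00, if a cycle counts when its 21 days have ended and only progression or death stops treatment. It is about 1.02–1.10 if the dose counts, and possibly below 1 if toxicity stops differ by arm. A single run of this trial could not distinguish such shifts from chance. The reason to act is that the output would be mislabelled, not that it would mislead by a known amount. The missing definition of a completed cycle is secondary. This is a change that should be made, not a flaw in the primary analysis.

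**What to change.** - **Aim.** Delete or reword the bullet in SAP 5.11.3.1 so that it does not claim to evaluate the effect of cycle number.
- **Reporting.** Present the ≥4, ≥5 and ≥6 cycle subsets and the monotherapy subset descriptively by arm, without between-arm p-values. This includes the PFS repeat in 5.11.3.2. Count time from the matching landmark or from the first monotherapy dose.
- **Label.** For example: *These subsets are selected after randomization. Results are descriptive and are not evidence on the effect of doxorubicin exposure or of monotherapy.*
- **Definition.** State whether a completed cycle means dose given or 21-day cycle ended.
- **Optional addition.** OS may be compared by assigned arm in all patients alive at a landmark, as a separate supportive analysis. Under a true hazard ratio of 1.00 it gives 0.99–1.00 in the frailty model. The SAP should say that it ignores cycles, drops early deaths and, if OS truly differs, conditions on survival (0.73–0.76 when the ITT hazard ratio is 0.723). It does not replace the cycle analysis.

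The cost is SAP wording, minor programming and the loss of p-values in these subsets.
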